sGLT2	Sodium-Glucose CoTransporter2.
SOP	Standard Operation Procedure
VGLUT	Vesicular Glutamate Transporters

Précis

Objective and Specific Aims: The objective of this proof-of-concept study is to demonstrate in non-diabetic men and women age ≥ 55 years that a sGLT2 inhibitor will increase ketone bodies and metabolites used for gluconeogenesis. We also hypothesize that sGLT2 inhibitor (empagliflozin) will increase circulating glucagon and fatty acids, decrease circulating amino acids, increase expression of receptors and mediators of ketone metabolism in plasma exosomes and change Magnetic Resonance Spectroscopy (MRS) brain metabolism measures.

Experimental Design and Methods: 10 men and 10 women will be recruited for this pilot study. Each eligible participant will have a screen visit (Visit 0) and three additional 2-day study visits (Visit 1-3). On Visits 1, 2 and 3, frequent blood sampling for β -hydroxybutyrate butyrate (β -OHB), acetoacetate, fatty and amino acids, glucagon, insulin and glucose levels will be carried out; these visits will also include blood work for exosome markers and brain MRS. In addition, placement of a continuous glucose monitor (CGM) along with a 34-hour urine collection will be carried out. On Visits 1 and 2 the participants will wear the CGM until they return for their next visit. On Visit 3 the CGM will be removed at the end of the study visit. On Visit 1, no empagliflozin will be administered. Participants will return in 13 +/- 2 days for Visit 2. Visit 2 is the same as Visit 1 except empagliflozin 25 mg will be administered both mornings, at least 30 minutes before eating breakfast and participants will continue empagliflozin 25 mg once every morning, at least 30 minutes before eating breakfast, at home until they return in 13 +/- 2 days for Visit 3. At the end of Visit 3, empagliflozin will be stopped.

Medical Relevance and Expected Outcome: Elevating ketone bodies may bolster neuronal health and delay onset and progression of cognitive impairment. The expected outcome of this study is that we will see an increase in circulating levels of ketones, glucagon and fatty acids, an increased expression of receptors and mediators of ketone metabolism in plasma exosomes and a change in Magnetic Resonance Spectroscopy (MRS) brain metabolism measures, in subjects taking a sGLT2 inhibitor. We expect circulating amino acid levels will decrease, especially during the overnight hours. This study will aid in deciding whether this class of compound may be used in a larger study to improve cognitive function in patients with diagnosis consistent with declining cognitive function. We require that empagliflozin be taken for up to 2 weeks before returning for Visit 3, because we need to fully understand the homeostatic adaptations that may occur in the metabolite response to empagliflozin due to prolonged (up to 2 weeks) sGLT2 inhibition. It is our goal in the future to use the information gathered in this pilot study to design a long-term study in people who actually suffer from mild cognitive impairment/AD and therefore a Visit 2 (34-hour acute study) only, as outlined above, would not give us the full picture of the metabolic changes that might occur with prolonged use, especially in a non-diabetic population.

1 Background Information and Scientific Rationale

1.1 Background and Rationale

Cognitive decline and Alzheimer's disease (AD) are leading sources of morbidity and mortality in the aging population. In the U.S. there were an estimated 4.7 million individuals over the age of 65 with clinical AD and the number is projected to rise to 13.8 million by 2050 (10). Currently, there is no cure for dementia and no ways to delay its onset or slow its progression in humans. Therefore, it is imperative that more research be focused on pathogenesis, pathophysiology and investigation of repurposing of drugs presently available so that treatments can be developed for managing dementia, and maybe at least preventing on-going neuronal functional decline. It is generally accepted that neurons use glucose as their primary source of energy. But neurons (as well as other cell types, such as heart muscle) can use ketone bodies (β -OHB, acetoacetate) that are generated by the liver and transported to extrahepatic tissue as an energy source. There are elements of glucose dysregulation and decreased uptake in neurons of people with dementia, especially Alzheimer's disease (AD). The high metabolic efficiency of ketone bodies had implications for brain because ketone bodies can be an energy source when glucose availability is limited due to a pathological event, such as AD.

SGLT2 inhibitors are now approved treatment for type 2 diabetes since 2016. They lower blood glucose because they allow glycosuria to occur due to glucose not being resorbed from the collecting tubules. This leads to loss of glucose from the body, resulting in lower blood glucose and weight loss. Additionally, empagliflozin, in a large multicenter study, has been shown to be beneficial in patients with known cardiac disease.

SGLT2 inhibitors would be expected to increase endogenous ketone bodies (β -OHB, acetoacetate) because when glucose is not resorbed back into circulation, glucagon levels in circulation become elevated and drive gluconeogenesis (GNG) in the liver. In order to provide substrate for GNG, lipolysis occurs, thereby supplying fatty acids for glucose and ATP formation. This should result in slightly increased ketone bodies in circulation, in particular during the overnight period. With this study, we wish to prove in the population who might benefit the most from increased endogenous ketone bodies whether this in fact occurs, and if it is sustainable – hence the need for at least the 14-day duration of treatment.

If SGLT2 inhibitors increase endogenous ketone bodies, then brain neurons and astrocytes may increase their metabolic reliance on ketone metabolism. This would be reflected in upregulation of monocarboxylate transporters (MCTs) required to import ketone bodies into the cell. MCT1 is not normally expressed in neurons or astrocytes, but it may be upregulated in astrocytes because of ketogenic diets.

(<https://www.proteinatlas.org/ENSG00000155380SLC16A1/tissue/cerebral+cortex#img>)¹.

On the other hand, MCT2 and MCT4 are highly expressed in neurons and would be expected to be upregulated with SGLT2 inhibitors

<https://www.proteinatlas.org/ENSG00000118596-SLC16A7/tissue/cerebral+cortex#img>;
<https://www.proteinatlas.org/ENSG00000141526-SLC16A3/tissue/cerebral+cortex#img>.

We can probe the expression of these transporters in neurons and astrocytes using plasma exosomes enriched for neuronal and astrocytic origin as a source of biomarkers ^{2,3}. Other neuronal markers that mediate the effects of ketogenic diet in epilepsy and may change with SGLT2 inhibitors are the metabotropic glutamate receptor (mGluR) and VGLUT, which may also be probed with neuronal-origin exosomes. Finally, we can measure EV biomarkers reflecting the status the insulin – Akt – mTOR signaling pathway that determines cell energy metabolism ³. These outcomes can be obtained through regular blood draws and shed light on the impact of the intervention on neuronal cellular metabolism.

Another methodology that can show changes in brain metabolism in response to SGLT2 inhibitors is brain Magnetic Resonance Spectroscopy (MRS). At the NIA 3T MRI Facility, we have the capacity to implement an advanced MRS method called J-PRESS. It can reliably detect previously elusive signals of important metabolites, such as glucose, lactate, ascorbate, as well as traditionally measured (but still important) metabolites, such as N-acetyl-aspartate (NAA) ⁴. Applying this technique on a voxel within the bilateral precuneus, a region known for its susceptibility to AD pathogenic processes, we recently showed large and significant elevations in glucose and lactate and reductions in N-acetyl aspartate (NAA) in AD subjects compared to both older and younger controls ⁴. In particular, NAA is a logical outcome for an intervention aiming to increase ketone availability and brain ketone utilization, since it was shown to increase in the hippocampus of mice consuming ketone esters ⁵. In addition, we have shown that functional connectivity within brain networks is related to MRS levels of neurotransmitters ⁶. To provide context and understand the impact of brain metabolic changes induced by SGLT2 inhibitors on brain function, resting fMRI will also be conducted. Any changes observed in these a priori hypothesized exosomal and MRS outcomes in this pilot study may be used to determine outcomes for future proof of concept studies of SGLT2 inhibitors in cognitive impairment and AD and inform the relevant power analyses.

1.2 Description of the Study

This pilot study is designed as a proof-of-concept study to examine the acute and chronic effects of a SGLT2 inhibitor (empagliflozin) on ketone body and metabolite production, as well as hormones directly involved in metabolism and nutrient utilization. This study will aid in deciding whether this class of compounds may be used for repurposing to improve cognitive function in patients with diagnosis consistent with declining cognitive function in a larger study.

2 Study Objectives

2.1 Primary Objective

To demonstrate that in non-diabetic humans, late middle-age to elderly, a sGLT2 inhibitor will increase ketone bodies, and metabolites used for GNG, especially during the night.

2.2 Secondary Objectives

- To determine the effects of such inhibition on a range of hormones and metabolites: insulin, glucagon, amino and fatty acid levels, especially overnight.
- To determine the effects of such inhibition on plasma exosomes biomarkers related to ketone metabolism (such as MCTs, receptors, intracellular mediators of insulin signaling and ketone metabolism).
- To determine the effects of such inhibition on brain MRS measures of neuronal integrity and metabolism (NAA, glucose, lactate).
- To investigate if this age group will tolerate this class of anti-diabetic drugs, for re-purposing.

3 Study Design

3.1 Description of the Study Design

This study involves a screening visit (Visit 0) and 3 study visits (Visits 1, 2 and 3) to the NIA Clinical Unit. In this pilot study, each enrolled participant will have a baseline visit (Visit 1) where no medication will be given and frequent blood draws x 34 hours for β -hydroxybutyrate butyrate (β -OHB), acetoacetate, fatty acids, glucagon, insulin and glucose levels will be done. Exosome studies, as well as brain MRS will also be done. The participant will have a continuous glucose monitoring system placed.

Visit 2 will take place in 13 +/-2 days from Visit 1. It will be the same as Visit 1, however, on Visit 2 participants will receive a daily (morning) oral dose of empagliflozin (Jardiance) 25 mg, followed by breakfast within 30 minutes. They will continue the daily dose of empagliflozin (Jardiance) 25 mg orally after discharge until they return for Visit 3 in 13 +/-2 days.

Visit 3 will be the same as Visit 2. At the end of Visit 3 the study drug will be discontinued, and the participant will have completed the study.

3.2 Study Endpoints

The primary study endpoint will be the level of circulating ketones on Visit 3 with a target of 1.5 times that of the participant's baseline (Visit 1). Other outcomes will be secondary.

4 Study Population

Twenty participants, ten males and ten females, age 55 and older will complete this pilot study. The ceiling for this study (100) reflects the additional accrual that we may anticipate. If needed, the protocol will be amended to account for an increase in the number of participants needed to be recruited.

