5.3 Visit 1 Baseline – No study medication given

At Visit 1, the enrolled participant will come to the NIA Clinical Research Unit for a two-day visit, lasting approximately 34 hours. The following procedures will be done:

- a. Height/weight, orthostatic blood pressure measurements, pulse, temperature, respirations and pulse oximetry.
- b. I.V. placement for fasting blood tests (fasting for at least 8 hours) including CMP, lipids, insulin and other hormones, and exosomes. Followed by blood sampling every 1.5-hours x 2, then q 1-hour x 1, then q 1.5-hours x 8, then q 2-hours x 4, then q 1.5-hours x 2, then q 1-hour x 1, then q 1.5-hours x 4 (completes 34-hours). This frequent sampling will include β -hydroxybutrate (β -OHB), acetoacetate, fatty and amino acids, glucagon, insulin and glucose levels. On Day 2, exosomes will be repeated and oxysterols and lipidomics will be drawn.
- c. Placement of a continuous glucose monitor (CGM) used to collect data for up to 14 days, worn by the participant until they return for Visit 2.
- d. 34-hour urine collection for creatinine clearance, C-peptide, and other hormones.
- e. Brain MRS and limited brain MRI for voxel placement, required anatomical studies and resting functional connectivity will be conducted.
- f. All meals will be provided. The meals on visits 1, 2 and 3 will be pre-selected by the participant. Food intake will aim to be uniform at all visits and at consistent times. Participants will be asked to record the time and items they eat on a Food Diary (Appendix C). They will also be instructed to hydrate. This includes drinking 8 ounces of water every 4 hours except when asleep.
- g. On the evening of Day 1, the participants will be given an activity monitor and will be instructed to walk 2,000 steps before bedtime.
- h. Discharge instructions will be given (Appendix D). They will wear the CGM and be asked to complete an Intake Diary (Appendix E) to record consuming anything other than water to assist with the CGM data collection.

5.4 Visit 2 occurs 13 +/- 2 days from Visit 1

Initiation of sGLT2 inhibitor (empagliflozin)

At Visit 2, the enrolled participant will come to the NIA Clinical Research Unit for a two-day visit, lasting approximately 34 hours. This visit will be the same as Visit 1, except the participant will receive a daily dose of empagliflozin (Jardiance).

The following procedures will be done:

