- l. A staff member will phone participants daily to assure they are taking the study medication and to assess for any symptoms. We will also remind them about the importance to hydrate, as stated above (f).

5.5 Visit 3 occurs 13 +/- 2 days from Visit 2

At Visit 3, the enrolled participant will come to the NIA Clinical Research Unit for a two-day visit, lasting approximately 34 hours. The following procedures will be done:

- a. Height/weight, orthostatic blood pressure measurements, pulse, temperature, respirations and pulse oximetry.
- b. I.V. placement for fasting blood tests (fasting for at least 8 hours) including CMP, lipids, insulin and other hormones. The study drug empagliflozin (Jardiance) will be administered at approximately 8:00 a.m. followed by blood sampling the same as visits 1 and 2. Breakfast will be given within 30 minutes of dosing.
- c. Placement of a continuous glucose monitor (CGM) used to collect data for up to 14 days, worn by the participant until the end of Visit 3.
- d. 34-hour urine collection for creatinine clearance, C-peptide, and other hormones.
- e. All meals will be provided. They will aim to be consistent items and times as what was consumed on Visits 1 and 2. Participants will be also be instructed to hydrate. This includes drinking 8 ounces of water every 4 hours except when asleep.
- f. On the evening of Day 1, the participants will be given an activity monitor and will be instructed to walk 2,000 steps before bedtime.
- g. Day 2: Participants will receive empagliflozin (Jardiance) 25 mg followed by breakfast within 30 minutes.
- h. Brain MRS and limited brain MRI for voxel placement, required anatomical studies and resting functional connectivity will be conducted.

- i. Following the final blood draw, participants will have completed the study. They will no longer take the study medication or wear the CGM.
- j. Discharge instructions will be given (Appendix G).

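### Does the 1.5-fold ketone target need a fixed sampling window, summary and combination rule before it can be used?

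*Combined protocol and SAP*

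**What the plan says.** Section 3.2 (Study Endpoints) defines the primary endpoint in one sentence, as the "level of circulating ketones on Visit 3 with a target of 1.5 times that of the participant's baseline (Visit 1"). All other outcomes are secondary. Section 4 plans for twenty completers.

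Section 1.1 says what is meant by ketones and when they should rise: "SGLT2 inhibitors would be expected to increase endogenous ketone bodies (β -OHB, acetoacetate"), giving "slightly increased ketone bodies in circulation, in particular during the overnight period". The primary objective in section 2.1 is that the drug "will increase ketone bodies, and metabolites used for GNG, especially during the night".

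Section 5.3 sets a fasting draw followed by a long timed series, ending "then q 2-hours x 4, then q 1.5-hours x 2, then q 1-hour x 1, then q 1.5-hours x 4 (completes 34-hours"). At Visit 3 (section 5.5) the drug "will be administered at approximately 8:00 a.m. followed by blood sampling the same as visits 1 and 2". The Day 2 dose carries no clock time: "Day 2: Participants will receive empagliflozin (Jardiance) 25 mg followed by breakfast within 30 minutes". Under Safety Labs in section 6.1, draws drop to 2-hourly if the blood count at Visit 2 or 3 has fallen by more than 10% from screening.

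Section 12 says that no power calculation can be done and adds text on enrollment and replacement. It names no analysis method. The Précis gives the purpose: "This study will aid in deciding whether this class of compound may be used in a larger study".

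**The concern.** A level at a visit with 23 draws could be a fasting value, an overnight mean, a 34-hour time-weighted mean or a peak. Twenty ratios could be combined as a geometric mean, an arithmetic mean or a count of participants who reach 1.5. The night emphasis in sections 1.1 and 2.1 has no clock limits and does not appear in section 3.2.

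The figure 1.5 is the only numerical target for the primary endpoint, and the study is meant to inform a decision about a larger one. If these choices are made after the data are seen, the target could be reported as met or missed on the same data.

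**Working it through.** **Schedule.** From section 5.3: 2×1.5 + 1×1 + 8×1.5 + 4×2 + 2×1.5 + 1×1 + 4×1.5 = 34 hours, which reproduces the plan's figure. Timed draws: 2 + 1 + 8 + 4 + 2 + 1 + 4 = 22, plus the fasting draw = 23. The 2-hourly fallback gives 34/2 + 1 = 18. If time 0 is 08:00, the 2-hourly block covers hours 16 to 24, that is 00:00 to 08:00, with five draws.

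**Choice of window.** The documents give no ketone levels, so the inputs here are assumptions. Take an 8-hour night, overnight ratio R, daytime ratio D and baseline night-to-day level k. Then

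34-hour ratio = (8kR + 26D) / (8k + 26), which equals 1.5 at k = 26(1.5 − D) / [8(R − 1.5)].

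| R | D | k=1 | k=2 | k=3 | k=4 | 34-hour ratio reaches 1.5 at |
|---|---|---|---|---|---|---|
| 2.0 | 1.0 | 1.24 | 1.38 | 1.48 | 1.55 | k = 3.25 |
| 1.6 | 1.0 | 1.14 | 1.23 | 1.29 | 1.33 | k = 16.25 |
| 2.0 | 1.2 | 1.39 | 1.51 | 1.58 | 1.64 | k = 1.95 |

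The overnight summary meets the target in every row. The 34-hour summary may not, but the conflict shrinks quickly once daytime ketones also rise.

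**Choice of combination rule.** Assume 20 lognormal ratios with true geometric mean g and log-ratio SD s.

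- Geometric mean reaches 1.5: 1 − Φ[ln(1.5/g)·√20/s].
- At least 11 of 20 reach 1.5: binomial tail with p = 1 − Φ[ln(1.5/g)/s].
- Arithmetic mean, and disagreement within the same trial: by simulation.

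| g | Quantity | s=0.2 | s=0.4 | s=0.6 | s=0.8 |
|---|---|---|---|---|---|
| 1.3 | Geometric mean ≥1.5 | <0.1% | 5% | 14% | 21% |
| 1.3 | At least 11 of 20 | 0.3% | 6% | 14% | 19% |
| 1.3 | Arithmetic mean ≥1.5 | 0.3% | 23% | 57% | 77% |
| 1.7 | Geometric mean ≥1.5 | 99.7% | 92% | 82% | 76% |
| 1.7 | At least 11 of 20 | 98% | 82% | 70% | 63% |

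The arithmetic mean stands apart because it estimates a different quantity. Its expected value is g·exp(s²/2), which at g = 1.3 is 1.33, 1.41, 1.56 and 1.79, so for the two larger SDs it truly exceeds 1.5. Within the same trial, the geometric mean and the majority count disagree in 0.3% to 14% of trials at g = 1.3 and in 2% to 20% at g = 1.7. A true ratio of exactly 1.5 is the hardest case: the geometric mean meets the target in 50% of trials and the count in 41%.

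**Precision at n = 20.** For an observed geometric mean of 1.5, the 95% interval is 1.5 × exp(±2.093·s/√20): 1.37–1.65, 1.24–1.81, 1.13–1.99 and 1.03–2.18 for the four SDs. Any sensible report would show this interval, and it says far more than whether the point estimate passed 1.5.

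**The case for a change.** The strongest case for a change is that pilot status excuses the missing power calculation but not an undefined primary endpoint. The protocol chose to set a number and links the study to a later decision. A definition would take only a little wording and no extra samples. There is also a practical reason for one: under the 2-hourly fallback, Visit 3 may have about 18 draws against 23 at Visit 1, so an unweighted mean would shift with the schedule alone.

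Much of this stands. The text is silent on all three choices, and writing them down before analysis would be good practice. It still does not show a fault in the plan:

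- No section names a daytime or whole-profile summary. The general sentence in section 6.2.1 listing ketones among fasting measures does not set an endpoint. The only time emphasis for ketones is the night, which gives an analyst a clear lead.
- The unequal number of draws is handled by a time-weighted mean, the usual summary for uneven sampling.
- Whether the hour-24 draw falls before or after the Day 2 breakfast is unstated. But meals are to be at consistent times at all visits, so a meal effect should largely cancel in a within-participant ratio.
- Any window fixed in advance would do, so the request is to record a choice, not to correct one.

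**Conclusion.** No change to the plan is needed. Section 3.2 leaves out detail but states nothing that gives a wrong answer. In a 20-person pilot with no stated test, error rate or go/no-go rule, the 1.5 target is a benchmark. A competent analyst would take β-OHB plus acetoacetate, form a time-weighted overnight mean at each visit, and report the geometric mean Visit 3/Visit 1 ratio with its 95% interval against 1 and 1.5. Other summaries would sit beside it.

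The choice of window could move an assumed doubling overnight to between 1.24 and 1.55 over 34 hours, and less of a gap remains if ketones also rise by day. The choice between geometric mean and majority count changes the answer in 0.3% to 14% of trials at a true ratio of 1.3 and 2% to 20% at 1.7. The much larger contrasts with the arithmetic mean come mostly from its targeting a different quantity. All these sizes rest on assumed night-to-day levels and log-ratio SDs of 0.2 to 0.8. They show that the reported result can flip, not how likely that is in this trial.

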4.1 Rationale for Subject Selection

This is a pilot study. We will enroll non-diabetic men and women age 55 and older. This age group is at greatest risk of cognitive decline. Therefore, the safety of sGLT2 inhibitors needs to be assessed in this non-diabetic population.

4.2 Recruitment Plan

Subjects will be recruited using multiple strategies, including but not limited to advertising in newspapers, flyers, Internet, NIH and NIA websites, expos and health fairs, volunteers who have expressed interest in NIA studies, and word of mouth from other study participants. All participants are recruited based on the same inclusion and exclusion criteria.

